#### **5.6.5 Physical Examination**

A physical examination, including vital signs measurements (blood pressure, pulse and temperature), will be performed according to the schedule of events. The physical examination should include a thorough evaluation of the subject's skin. Any clinically significant abnormalities discovered during physical examinations after the Screening / Baseline visit should be documented and evaluated as potential adverse events.

### **5.6.6 Investigator's Global Assessment for Prurigo Nodularis (IGA-PN)**

IGA-PN will be determined for all subjects at all visits during the study. Investigator's global assessment for prurigo nodularis (IGA PN) is a clinician-reported outcome that allows clinicians to assess the activity of PN (IGA PN-A) using a 5-point scale from 0 (clear) to 4 (severe); and the stage of the disease (IGA PN-S) using a 5-point scale from 0 (clear) to 4 (severe). [See Appendix A](#)

### **5.6.7 Patient Reported Outcomes**

Subjects will complete the PRO's according to the schedule of assessments. Questionnaires should be prior to medical procedures and clinical evaluations.

#### **5.6.7.1 Worst-Itch Numerical Rating Scale**

(WI-NRS) is a PRO comprised of a single item rated on a scale from 0 ("No itch") to 10 ("Worst imaginable itch"). Participants are asked to rate the intensity of their worst pruritus (itch) over the past 24 hours using this scale. 0.1 Worst Itch Numeric Rating Scale. [See Appendix B](#)

#### **5.6.7.2 Dermatology Life Quality Index**

Dermatology Life Quality Index (DLQI) to assess symptoms and impacts of dermatologic diseases on quality of life. [See Appendix C](#)

### **5.6.8 Early Discontinuation Procedures**

Subjects will be prematurely discontinued from the study under the following conditions:

1. Subject requests to withdraw from the study.
2. Subject experiences an adverse event that makes it difficult or intolerable for the subject to continue treatment, or increases risk to the subject, or interferes with the investigator's ability to clinically evaluate the progress of the subject's treatment.
3. Subject begins an unapproved concomitant therapy for prurigo nodularis, atopic dermatitis or another medical condition that may increase risk to the subject if continuing study treatment.
4. Subject cannot be reached / lost to follow-up.
5. The study investigator suspends or terminates the study.
6. Other unanticipated reason.

Any subject who prematurely discontinues the study should complete the week 24 (End of Study) assessments.

## **6 COMPLAINTS/ADVERSE EVENTS/SERIOUS ADVERSE EVENTS**

Adverse events will be collected from the time of the first dose of product during the study until 30 days following the intake of the last dose taken during the study period. An AE is defined as any untoward medical occurrence in a subject or clinical investigation subject administered a pharmaceutical product and which does not necessarily have a causal relationship with this treatment. An AE can therefore be any unfavorable and unintended sign (including an abnormal laboratory finding), symptom, or disease temporally associated with the use of a medicinal (investigational) product, whether or not the event is considered causally related to the use of the product.

Such an event can result from use of the drug as stipulated in the protocol or labeling, as well as from accidental or intentional overdose, drug abuse, or drug withdrawal. Any worsening of a pre-existing condition or illness is considered an AE. Worsening in severity of a reported AE should be reported as a new AE. Laboratory abnormalities and changes in vital signs are considered to be AEs only if they result in discontinuation from the study, necessitate therapeutic medical intervention, meets protocol specific criteria and/or if the investigator considers them to be AEs.

The investigator will monitor each subject for clinical and laboratory evidence of AEs on a routine basis throughout the study. All AEs will be followed to a satisfactory conclusion. An elective surgery/procedure scheduled to occur during a study will not be considered an AE if the surgery/procedure is being performed for a pre-existing condition and the surgery/procedure has been preplanned prior to study entry. Elective surgery will not be allowed during the study until the primary endpoint has been assessed (Week 16). However, if the pre-existing condition deteriorates unexpectedly during the study (e.g., surgery performed earlier than planned), then the deterioration of the condition for which the elective surgery/procedure is being done will be considered an AE. If any of the following events are reported, then the following supplemental form must be completed. If an AE meets any of the following criteria, it is to be reported to AbbVie as an SAE within 24 hours of the site being made aware of the SAE:

Death of Subject- An event that results in the death of a subject.

**Life-Threatening-** An event that, in the opinion of the investigator, would have resulted in immediate fatality if medical intervention had not been taken. This does not include an event that would have been fatal if it had occurred in a more severe form.

**Hospitalization or Prolongation of Hospitalization-** An event that results in an admission to the hospital for any length of time or prolongs the subject's hospital stay. This does not include an emergency room visit or admission to an outpatient facility.

**Congenital Anomaly-** An anomaly detected at or after birth, or any anomaly that results in fetal loss.

**Persistent or Significant Disability/Incapacity-** An event that results in a condition that substantially interferes with the activities of daily living of a study subject. Disability is not intended to include experiences of relatively minor medical significance such as headache, nausea, vomiting, diarrhea, influenza, and accidental trauma (e.g., sprained ankle).

**Important Medical Event Requiring Medical or Surgical Intervention to Prevent Serious Outcome-** An important medical event that may not be immediately life threatening or result in death or hospitalization, but based on medical judgment may jeopardize the subject and may require medical or surgical intervention to prevent any of the outcomes listed above (i.e., death of subject, life threatening, hospitalization, prolongation of hospitalization, congenital anomaly, or persistent or significant disability/incapacity). Additionally, any elective or spontaneous abortion or stillbirth is considered an important medical event. Examples of such events include allergic bronchospasm requiring intensive treatment in an emergency room or at home, blood dyscrasias or convulsions that do not result in inpatient hospitalization, or the development of drug dependency or drug abuse.

**Special Situations** - accidental or intentional overdose, medication error, occupational or accidental exposure, off-label use, drug abuse, drug misuse, lack of efficacy, or drug withdrawal must be reported to AbbVie within 30 calendar days.

All AEs reported from the time of study drug administration until 30 days after discontinuation of study drug administration will be collected, whether solicited or spontaneously reported by the subject. In addition, SAEs and protocol-specified

nonserious AEs will be collected from the time the subject signs the study-specific informed consent. Adverse events will be monitored throughout the study to identify any of special interest that may indicate a trend or risk to subjects.

### Adverse Events of Special Interest

The following AESIs will be monitored during the study:

- Serious infections
- Opportunistic infections
- Herpes zoster
- Tuberculosis
- Malignancy (all types)
- GI perforations
- Adjudicated cardiovascular events (e.g., major adverse cardiovascular event [MACE])
- Anemia
- Neutropenia
- Lymphopenia
- Increased serum creatinine and renal dysfunction
- Hepatic events and increased hepatic transaminases
- Elevated creatine phosphokinase
- embolic and thrombotic events (non-cardiac, non-central nervous system)

### Adverse Event Severity and Relationship to Study Drug

The investigators will rate the severity of each AE according to the National Cancer Institute Common

Terminology Criteria for Adverse Events version 4.03.

If no grading criteria are provided for the reported event, then the event should be graded follows:

Mild (Grade 1) Asymptomatic or mild symptoms; clinical or diagnostic observations only; intervention not indicated

Moderate (Grade 2) Minimal, local or noninvasive intervention indicated; limiting age-appropriate instrumental activities of daily living (ADL)

Severe (Grade 3 to 5) Grade 3 Severe or medically significant but not immediately life-threatening; hospitalization or prolongation of hospitalization indicated; disabling; limiting self-care ADL (selfcare ADL refer to bathing, dressing and undressing, feeding self, using the toilet, taking medications, and not bedridden)

Grade 4 Life-threatening consequences; urgent intervention indicated

Grade 5 Death related to AE

The investigator will use the following definitions to assess the relationship of the AE to the use of study drug:

Reasonable Possibility – After consideration of factors including timing of the event, biologic plausibility, clinical judgment, and potential alternative causes, there is sufficient evidence (information) to suggest a causal relationship.

No Reasonable Possibility – After consideration of factors including timing of the event, biologic plausibility, clinical judgment, and potential alternative causes, there is insufficient evidence (information) to suggest a causal relationship. For causality assessments, events assessed as having a reasonable possibility of being related to the study drug will be considered "associated." Events assessed as having no reasonable possibility of being related to study drug will be considered "not associated." In addition, when the investigator has not reported a causality or deemed it not assessable, AbbVie will consider the event associated.

If an investigator's opinion of no reasonable possibility of being related to study drug is given, an Other cause of event must be provided by the investigator for the SAE.

### Pregnancy

While not an AE, pregnancy in a study subject must be reported to AbbVie within 1 working day after the site becomes aware of the pregnancy. If a pregnancy occurs in a study subject or in the partner of a study subject, information regarding the pregnancy and the outcome will be collected. In the event of pregnancy occurring in a subject's partner during the study, written informed consent from the partner must be obtained prior to collection of any such information. AbbVie will provide a separate consent form for this purpose. Pregnancy in a subject's partners will be collected from the date of the first dose through 30 days following the last dose of study drug. Subjects should avoid pregnancy throughout the course of the study, starting with the Screening Visit through 30 days after the last study drug administration for female subjects. Results of a positive pregnancy test or confirmation of a pregnancy will be assessed starting with the Screening Visit through the final study visit. Subjects who become pregnant during the study must be

discontinued. The pregnancy outcome of an elective or spontaneous abortion, stillbirth or congenital anomaly is considered a SAE and must be reported to AbbVie within 24 hours after the site becomes aware of the event.

## **7 INVESTIGATIONAL PRODUCT HANDLING**

### **7.1 Investigational Product Receipt**

At study initiation and as needed thereafter, upadacitinib 15mg will be shipped to a responsible person at the investigator's institution, who will check the amount and condition of the drug, and maintain a record of this information. The master accountability log will be maintained by un-blinded pharmacy staff.

### **7.2 Investigational Product Storage**

Investigational product will be stored per the storage conditions identified on drug label. At the study site, all IP will be stored in a locked, safe area to prevent unauthorized access. Records of the actual storage conditions during the period of the study will be maintained.

## **8 RECORD RETENTION**

The investigator must retain these documents according to local laws or requirements. Essential documents include, but are not limited to, the following:

- Signed informed consent documents for all subjects;
- Subject identification code list, screening log (if applicable), and enrollment log;
- Record of all communications between the Investigator and the IRB/EC;  
Composition of the IRB/EC; g
- Record of all communications between the Investigator and Abbvie.
- List of Sub-investigators and other appropriately qualified persons to whom the Investigator has delegated significant study-related duties, together with their roles in the study, curriculum vitae, and their signatures;
- Copies of CRFs (if paper) and of documentation of corrections for all subjects;
- IP accountability records;
- All other source documents (subject records, hospital records, laboratory records, etc);

- All other documents as listed in Section 8 of the ICH consolidated guideline on GCP (Essential Documents for the Conduct of a Clinical Trial).

The Investigator must notify Abbvie if he/she wishes to assign the essential documents to someone else, remove them to another location or is unable to retain them for a specified period. If the Investigator is unable to meet this obligation, the Investigator must ask Abbvie for permission to make alternative arrangements. Details of these arrangements should be documented. All study documents should be made available if required by relevant health authorities. Investigator/Institution should take measures to prevent accidental or premature destruction of these documents.

To protect subjects' confidentiality, all subjects and their associated samples will be assigned numerical study identifiers or "codes." No identifiable information will be provided to Abbvie.

## **8.1 Study Monitoring**

The investigator will self-monitor all study records for accuracy, completeness, and compliance with the protocol and GCPs and federal regulations. All study records will be made available to Abbvie representatives upon request. Study site facilities and study records will be made available to regulatory authorities' inspectors if an inspection takes place. The investigator will notify Abbvie if this occurs.

## **8.2 Statistics**

It is desired to enroll 25 patients.

Primary Endpoint: Proportion of participants with improvement (reduction) in worst-itch numeric rating scale (WI-NRS) by  $\geq 4$  from baseline to Week 16 [Time Frame: Baseline to Week 12] WI-NRS is a patient-reported outcome (PRO) comprised of a single item rated on a scale from 0 ("No itch") to 10 ("Worst imaginable itch").

Secondary Endpoints: Percent improvement (reduction) in worst-itch numeric rating scale (WI-NRS) by  $\geq 4$  from baseline to Week 24

IGA PN-S 0 or 1 at weeks 12 & 24

IGA PN-A 0 or 1 at week 12 & 24

Percent improvement of PN-S & PN-A at week 12 & 24

DLQI improvement at weeks 12 & 24

Adverse Events

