Study Endpoints	Primary Endpoint: Proportion of participants with improvement (reduction) in worst-itch numeric rating scale (WI-NRS) by $\geq 4$ from baseline to Week 12. [Time Frame: Baseline to Week 12 ]WI-NRS is a patient-reported outcome (PRO) comprised of a single item rated on a scale from 0 ("No itch") to 10 ("Worst imaginable itch). Secondary Endpoints: Proportion of patients with improvement in worst-itch numeric rating scale (WI-NRS) by $\geq 4$ from baseline to Week 24 IGA PN-S 0 or 1 at weeks 12 & 24 IGA PN-A 0 or 1 at week 12 & 24 Percent improvement of PN-S & PN-A at week 12 & 24 DLQI improvement at weeks 12 & 24 Adverse Events
References	Tessa B. Mullins, Poonam Sharma, Christopher A. Riley, Sidharth Sonthalia. Prurigo Nodularis. StatPearls [Internet]. Treasure Island (FL): StatPearls Publishing; 2021 Jan. 2020 Sep 15.  Eric H Kowalski, Diana Kneiber, Manuel Valdebran, Umangi Patel, Kyle T Amber. Treatment-resistant prurigo nodularis: challenges and solutions. Clin Cosmet Investig Dermatol. 2019 Feb 28;12:163-172. doi: 10.2147/CCID.S188070. eCollection 2019.

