#### **5.5.1.3 Upadacitinib Dosage Adjustments**

Upadacitinib will be dispensed and administered as 15mg QD at baseline. For subjects who do not achieve  $\leq$  2-point reduction in itch at week 8, upadacitinib dosage will be increased to 30mg QD. The investigator may reduce the dose to 15mg QD after week 16 per investigator discretion. If an SAE or an adverse event that is thought to be related to study drug and is not alleviated by symptomatic intervention, study drug will be discontinued. Subjects who permanently discontinue study drug under this protocol should receive standard care of prurigo nodularis treatment as prescribed by their physician.

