### **8.2.1 Additional Statistical Considerations**

The objective of the statistical analyses is to assess the efficacy and safety of upadacitinib for the treatment of subjects with moderate to severe PN who are candidates for systemic therapy. The Primary Analysis for all efficacy endpoints will be conducted after all continuing subjects have completed the study activities up to Week 16. The Intent-to-Treat (ITT) Population consists of all randomized subjects and will be used for the efficacy analyses. A Per-Protocol Population may be defined if deemed necessary to exclude subjects with major protocol violations. The criteria to define the Per-protocol Population will be detailed in the SAP. Subjects to be excluded from the Per-Protocol Population will be finalized before week 16. The Per-Protocol Population, if defined, will be used to analyze the primary efficacy endpoint.

The Safety Population consists of all randomized subjects who received at least 1 dose of study drug. An All Upadacitinib Treated Population consists of all subjects who received at least one dose of upadacitinib in the study. This population will be used to provide a comprehensive summary of safety.

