### **8.3 Schedule of Events**

	V1	V2	V3	V4	V5	V6	V7	V8
Procedures/Non-Procedure Description	SCR	BL	WK4	WK8	WK12	WK16	WK20	WK24
Informed Consent	X							
Medical History and Demographics	X	X						
Inclusion/Exclusion Criteria	X	X						
Prior/Concurrent Medications/Procedures	X	X	X	X	X	X	X	X
Physical Examination	X	X	X	X	X	X	X	X
Serum Pregnancy	X							
Hepatitis B & C profile. Quantiferon Gold	X							
Safety Labs	X					X		X
Urine Pregnancy Test		X	X	X	X	X	X	X
Safety / AE Assessment	X	X	X	X	X	X	X	X
Patient Reported Outcomes / Questionnaires		X	X	X	X	X	X	X
Clinical Severity / Efficacy Assessments	X	X	X	X	X	X	X	X
Pharmacy Dispense/Drug Accountability			X	X	X	X	X	X

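### The primary itch endpoint is set at Week 12 in the synopsis, at both Week 16 and Week 12 in Section 8.2, and at Week 16 in Section 6, and nothing says which governs

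*Combined protocol and SAP*

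**What the plan says.** Three places attach a week to the primary endpoint, and they do not agree.

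- **Synopsis, Study Endpoints:** Week 12, in both the definition and its time frame ("from baseline to Week 12. [Time Frame: Baseline to Week 12").
- **Section 8.2 Statistics:** Week 16 in the definition, Week 12 in the time frame ("from baseline to Week 16 [Time Frame: Baseline to Week 12").
- **Section 6:** elective surgery is not allowed "until the primary endpoint has been assessed (Week 16"), which ties Week 16 to the endpoint itself.

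Section 8.2.1 adds two timing rules. On the analysis: "The Primary Analysis for all efficacy endpoints will be conducted after all continuing subjects have completed the study activities up to Week 16". On the optional Per-Protocol set: "Subjects to be excluded from the Per-Protocol Population will be finalized before week 16".

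The Schedule of Events (Section 8.3) marks the row "Patient Reported Outcomes / Questionnaires" at every visit from baseline to Week 24, so itch is recorded at both candidate weeks. The secondary efficacy endpoints fall at Weeks 12 and 24, or at Week 24 alone for itch. None is at Week 16.

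**The concern.** A primary endpoint with two possible weeks gives two possible headline results, and a reader could not tell whether the week reported was the week planned. The trial has one arm, no blinding and one centre. Section 8.1 states that "The investigator will self-monitor all study records for accuracy, completeness, and compliance with the protocol". Site staff will see itch scores as they accrue, and the text would not stop the week being settled after both proportions are known.

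The two weeks also measure different things. Under Section 5.5.1.3, for some subjects, depending on itch response "at week 8, upadacitinib dosage will be increased to 30mg QD". Those subjects have had about 12 − 8 = 4 weeks on the higher dose at Week 12 and about 16 − 8 = 8 weeks at Week 16.

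Two consequences follow from Section 8.2.1. An analysis of all efficacy endpoints at Week 16 would have incomplete data for the Week 24 secondary endpoints. And if the primary week is 12 and a Per-Protocol set is defined, exclusions could still be decided after Week 12 outcomes are available.

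**Working it through.** **Consistency check.** Each statement of timing, side by side:

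| Place | Week | Attached to |
|---|---|---|
| Synopsis, definition and time frame | 12 | the endpoint |
| Section 8.2, definition | 16 | the endpoint |
| Section 8.2, time frame | 12 | the endpoint |
| Section 6 | 16 | the endpoint |
| Section 8.2.1, primary analysis | 16 | a data cut |
| Section 8.2.1, Per-Protocol list | before 16 | a data cut |

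The Section 8.2.1 entries can serve either week, because a cut at Week 16 includes Week 12. The contradiction therefore rests on the first four rows, which cannot all be true.

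**Plan's own figure.** The only relevant number is the target of 25 subjects. No assumed response, precision, alpha or power accompanies it, so there is nothing to reproduce.

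**Size of the possible bias.** Inputs that are assumptions, not document figures:

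- all 25 subjects evaluable at both weeks;
- the same true response p at both weeks, from 0.3 to 0.6;
- correlation φ between a subject's responder status at the two weeks, from 0.3 to 0.9.

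The probability of responding at Week 12 only equals that of responding at Week 16 only:

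p10 = p01 = p(1 − p)(1 − φ).

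Let D be the Week 12 responder count minus the Week 16 count. The larger count is half of (sum of counts + |D|), so reporting the better week overstates response on average by

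E|D| / (2n).

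*Worked case, p = 0.5 and φ = 0.5.* p10 = 0.5 × 0.5 × 0.5 = 0.125. The variance of D is 25 × 2 × 0.125 = 6.25, so its SD is 2.5. A normal approximation gives E|D| ≈ 0.798 × 2.5 = 1.995 and a bias of about 1.995/50 = 3.99 points. Exact enumeration gives 3.93.

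Exact results, average overstatement in percentage points:

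| p | φ = 0.3 | φ = 0.5 | φ = 0.7 | φ = 0.9 |
|---|---|---|---|---|
| 0.3 | 4.27 | 3.59 | 2.73 | 1.40 |
| 0.4 or 0.6 | 4.58 | 3.85 | 2.93 | 1.54 |
| 0.5 | 4.68 | 3.93 | 3.00 | 1.58 |

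Probability that the weeks differ by 2 or more subjects (2/25 = 8 points):

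| p | φ = 0.3 | φ = 0.5 | φ = 0.7 | φ = 0.9 |
|---|---|---|---|---|
| 0.3 | 0.577 | 0.506 | 0.381 | 0.127 |
| 0.4 or 0.6 | 0.603 | 0.535 | 0.415 | 0.151 |
| 0.5 | 0.611 | 0.544 | 0.426 | 0.158 |

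The two counts differ at all with probability 0.553 (p = 0.3, φ = 0.9) to 0.865 (p = 0.5, φ = 0.3).

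A separate simulation over φ of 0.5 to 0.9 gave the same biases to rounding. At p = 0.5, the chance that the lower limit of the exact 95% interval lies above the true response rose from 2.2% for one fixed week to between 3.0% and 4.0% for the better week.

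**Against sampling error.** The exact (Clopper-Pearson) 95% interval for 12/25 (48%) is 27.8% to 68.7%, a half-width of (68.7 − 27.8)/2 ≈ 20 points.

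**The case against.** The strongest reply is that Week 12 is plainly meant. The synopsis says it twice, and the Section 8.2 time frame repeats it. The other efficacy measures are listed at Weeks 12 and 24 while the secondary itch endpoint is at Week 24 only, so a Week 12 primary fills exactly that gap. This makes Week 12 the better reading, but it does not remove Week 16 from the Section 8.2 definition or from Section 6, and the protocol does not say which week is left over.

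Second, the bias arises only if someone picks the week on the results. The documents plan no such thing, and if one week is fixed for another reason the selection bias is zero. Even under selection, the counts tie in about 13% to 45% of trials and nothing changes. That is right: the finding concerns opportunity, not intent.

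Third, the figures depend on assumptions. With correlation limited to 0.5–0.9 the range is 1.4 to 3.9 points. Equal true response ignores any real change after the Week 8 dose rule. With no imputation (Statistical Analyses for Efficacy), the evaluable number may differ between weeks. These limits stand, and the figures are illustrative.

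Fourth, the Week 8 rule shows only that Week 8 itch is read, and Section 8.1 also opens the records to the funder and to inspectors. Both points are fair. The open-label design carries the argument.

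Last, the trial is exploratory, with no test or success threshold. No formal error rate is therefore inflated, and the case rests on the contradiction rather than on the size of the bias.

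**Conclusion.** The concern holds and must be fixed. The current text gives the primary endpoint two weeks and no rule for choosing between them. As it stands, the trial could not show that its headline proportion was the one planned. If the better week were reported, response would be overstated by 1.4 to 4.7 points on average under the stated assumptions (25 evaluable subjects, equal true response of 30–60%, correlation 0.3–0.9). This is small beside a half-width of about 20 points, but it runs in one direction and the confidence interval does not show it. Any true difference between the weeks after the dose change would come on top and has not been quantified.

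**What to change.** Before outcomes are reviewed:

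1. Name one primary week and use it in the synopsis, Section 8.2 and Section 8.2.1. Week 12 fits the synopsis, the Section 8.2 time frame and the secondary schedule.
2. Report itch response at the other week as supportive only.
3. State in Section 8.2.1 that Week 24 endpoints are analysed after the last Week 24 visit.
4. If a Per-Protocol set is used, freeze its list before outcomes at the primary week are reviewed.
5. Reconcile the week in Section 6 with the chosen endpoint. How long elective surgery is restricted is for the sponsor and investigator to decide; no period is proposed here.

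The cost is a text amendment, with no extra visits or subjects. While the text is open, a separate mismatch also needs reconciling: Section 5.6.4 places on-treatment safety laboratory tests at Weeks 12 and 24, and the Schedule of Events at Weeks 16 and 24. It plays no part in this finding.

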### **5.2.1 Inclusion Criteria**

Patients who meet all of the following criteria will be enrolled in the study:

1. Male or female adult 18- 64 years of age at time of screening.
2. Diagnosis of prurigo nodularis for  $\geq$  3 months
3. Moderate-to-Severe prurigo nodularis as determined by at least 10 PN lesions on legs and/or arms and/or trunk at screening and baseline.
4. Failure of at least a 2 week course of medium to super potent TCS or TCS is not medically advisable for subject.
5. Females of childbearing potential must not have a positive serum pregnancy test at the Screening Visit and must have a negative urine pregnancy test at the Baseline Visit prior to study drug dosing. Note: subjects with borderline pregnancy test at Screening must have a serum pregnancy test  $\geq$  3 days later to determine eligibility. If female, subject must be postmenopausal OR permanently surgically sterile OR for females of childbearing potential practicing at least one protocol specified method of birth control, that is effective from the Baseline Visit through at least 30 days after the last dose of study drug. Female subject must not be pregnant, breastfeeding or considering becoming pregnant during the study or for approximately 30 days after the last dose of the study drug.
6. Subject is a candidate for systemic therapy
7. Able and willing to give written informed consent prior to performance of any study-related procedures.
8. Subject must be in general good health as judged by the Investigator, based on medical history, physical examination.

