## 7. APPENDICES

### Appendix A

### INVESTIGATOR'S GLOBAL ASSESSMENT OF PRURIGO NODULARIS: ACTIVITY AND STAGE

Score	Category	Description: Activity (IGA PN-A)
0	Clear	No nodules have excoriations or crusts

1	Almost Clear	Very small proportion of nodules have excoriations or crusts (up to approximately 10% of all nodules)
2	Mild	Minority of nodules have excoriations or crusts (approximately 11-25% of all nodules)
3	Moderate	Many nodules have excoriations or crusts (approximately 26-75% of all nodules)
4	Severe	Majority of nodules have excoriations or crusts (approximately 26-75% of all nodules)

Score	Category	Description: Stage (IGA PN-S)
0	Clear	No nodules (0 nodules)
1	Almost Clear	Rare, flattened lesions, with no more than 5 dome-shaped palpable nodules (approximately 1-5 nodules)
2	Mild	Few, mostly flattened lesions, with small number of dome-shaped palpable nodules (approximately 6-19 nodules)
3	Moderate	Many lesions, partially flattened, and dome-shaped palpable nodules (approximately 20-100 nodules)
4	Severe	Abundant lesions, majority are dome-shaped palpable nodules (over 100 nodules)

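### The percent-improvement endpoint for PN-S and PN-A has no formula; read as percent change in a 0-4 grade, it depends on baseline grade and cannot be computed when baseline PN-A is 0

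*Combined protocol and SAP*

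**What the plan says.** The Synopsis (Study Endpoints) and section 8.2 Statistics carry the same secondary endpoint: "Percent improvement of PN-S & PN-A at week 12 & 24". Neither place, nor section 8.2.1, gives a formula, a summary statistic or a rule for a baseline of zero.

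The only PN-S and PN-A measures in the protocol are the two investigator global assessments of section 5.6.6 and Appendix A. Each has five ordered categories, 0 to 4, and is rated at every visit.

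- **PN-S** (stage) follows nodule numbers. Grade 2 is about 6 to 19 nodules and grade 3 about 20 to 100.
- **PN-A** (activity) follows the share of nodules that are excoriated or crusted. Its grade 0 reads "No nodules have excoriations or crusts", so nodules may be present at grade 0 as long as none is excoriated or crusted.

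Severity for entry is set by lesion count alone (section 5.2.1, criterion 3): "Moderate-to-Severe prurigo nodularis as determined by at least 10 PN lesions on legs and/or arms and/or trunk at screening and baseline". No criterion sets a minimum IGA grade. Section 8.2.1 puts all efficacy endpoints on the ITT population and applies no imputation.

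**The concern.** A percent change treats grade labels as amounts measured from a true zero. These labels are ordered categories of unequal width, so dividing by the baseline label gives the same one-grade move a different score depending on where the subject started. The mean then partly describes how mild the enrolled subjects were. With a single arm, no control group with a similar baseline mix can offset this.

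The second problem is the zero baseline. Because entry counts lesions and not excoriations, a subject can start at PN-A 0. Percent change does not exist for that subject, and the plan does not say what happens. By default the subject leaves this endpoint, and any later worsening in activity leaves it too.

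**Working it through.** The plan attaches no power, test or expected value to this endpoint, so there is no stated figure to reproduce.

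**1. Score for a one-grade gain.** Assumed formula, since none is written: percent improvement = 100 x (baseline - follow-up) / baseline.

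| Baseline to follow-up | Calculation | Percent improvement |
|---|---|---|
| 4 to 3 | 100 x 1/4 | 25.0 |
| 3 to 2 | 100 x 1/3 | 33.3 |
| 2 to 1 | 100 x 1/2 | 50.0 |
| 1 to 0 | 100 x 1/1 | 100.0 |
| 0 to any grade | divisor is 0 | undefined |

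The scale is also lopsided. A worsening from 1 to 4 scores 100 x (1 - 4)/1 = -300%. Among 25 subjects, one such value lowers the mean by 300/25 = 12 points compared with no change in that subject.

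**2. Which baselines the entry rule allows.**

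- PN-A: ten or more lesions, none excoriated or crusted, meets criterion 3 and is grade 0. Baselines 0 to 4 are all open, so the whole table applies.
- PN-S: if the 10 lesions count as nodules, they already fall in the band of about 6 to 19, which is grade 2. Baselines are then 2 to 4, the range is 25% to 50%, and a zero baseline cannot occur.

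**3. Effect of baseline mix on the mean.** The mixes below are assumptions, because the documents give no baseline distribution. All 25 subjects gain exactly one grade.

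| Subjects at grade 2 / 3 / 4 | Calculation | Mean |
|---|---|---|
| 2 / 8 / 15 | (2x50 + 8x33.3 + 15x25)/25 | 29.7% |
| 5 / 15 / 5 | (5x50 + 15x33.3 + 5x25)/25 | 35.0% |
| 15 / 8 / 2 | (15x50 + 8x33.3 + 2x25)/25 | 42.7% |

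The spread is 42.7 - 29.7 = 13.0 points. The outer limits for baselines 2 to 4 are 25.0% (all at 4) and 50.0% (all at 2).

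**4. Chance of meeting a zero baseline.** The documents give no frequency for PN-A 0 at entry. For an assumed frequency p, the chance of at least one such subject among 25 is 1 - (1 - p)^25:

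| Assumed p | 1% | 2% | 5% | 10% |
|---|---|---|---|---|
| Chance of at least one | 22% | 40% | 72% | 93% |

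**5. Scale definition.** Appendix A gives PN-A grades 3 and 4 the same band, about 26-75% of nodules. The percentage therefore does not separate 4 from 3, and that step counts as improvement under percent change and under any one-grade rule.

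**The case against.** Several objections have force.

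- **No computation is written.** A reader might infer that the plan specifies percent change in grade. It does not. Section 8.2 uses the words percent improvement for the WI-NRS endpoint (a drop of at least 4 points) that the Synopsis calls a proportion of patients, so the PN-S and PN-A line could mean the percent of subjects improved. Percent change is still the more natural reading, because the responder versions (grade 0 or 1) are listed separately and the Synopsis uses both terms. If a proportion was meant, the threshold for improvement is missing. The endpoint is undefined on either reading.
- **The spread is not a pure artefact.** A reader might take the 13 points as the error from the metric under one identical drug effect. That does not follow: if the grades are of unequal width, one grade is not the same effect at each baseline. The mixes are also assumed, and the two outer ones are near mirror images. The figure illustrates sensitivity to baseline and is not an estimate of bias.
- **The subject is not lost to the study.** The endpoints of PN-S and PN-A grade 0 or 1 need no baseline divisor. A subject who starts at PN-A 0 and worsens to grade 2 or more appears there as a non-responder. Those endpoints do not fully cover the gap, however: a subject who enters at PN-A 0 or 1 meets the PN-A one without changing.
- **A zero baseline may be rare.** Section 5.1 describes subjects as having moderate-to-severe itch, and such subjects may usually have excoriations. The documents do not settle this.
- **The replacement is imperfect.** The proportion improving by at least one grade also treats 4 to 3 and 2 to 1 alike, and it depends on how many subjects start at 0. It does not show worsening. The shift table does, so the two belong together.

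**Conclusion.** The point holds as a minor improvement. What the documents establish is a secondary endpoint without a formula, on ordered 0-4 grades, with no rule for a zero baseline that the entry criteria allow on PN-A. Everything further rests on reading it as percent change in grade. On that reading:

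- the 25% to 100% range and the undefined case belong to PN-A only;
- PN-S runs from about 25% to 50%, provided entry lesions count as nodules;
- a subject starting at PN-A 0 drops out of this one ITT endpoint and of no other.

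A reader might go on to conclude that the result could not be compared with other studies. The documents do not show how other studies scored these scales, so that is not claimed. Nor is any inference at risk: the study is exploratory, has one arm and attaches no test to this endpoint. The case for acting is that descriptive summaries are the study's main output, and this one can be made well defined at almost no cost.

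**What to change.** In the Synopsis and section 8.2, replace the endpoint with the following, for PN-S and PN-A separately at Weeks 12 and 24:

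1. a shift table of baseline grade against grade at the visit;
2. the number and proportion of ITT subjects whose grade is at least one lower than at baseline. Subjects with baseline grade 0 stay in the denominator as not improved, and any worsening in them is read from the shift table.

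If percent change is kept, write the formula, label it descriptive and report how many subjects were excluded because their baseline was 0.

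Before one-grade changes on PN-A are counted, correct Appendix A so that grades 3 and 4 no longer share one percentage band. If ratings have already been made, record which description the raters used.

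The cost is a wording change and one shift table per scale. IGA-PN is already rated at every visit, so no new data are needed. The sponsor gives up a single headline percentage.
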